#### **8.3 Randomization Code Creation and Storage**

Randomization personnel of the sponsor or designee will generate the randomization schedule. Randomization information will be stored in a secured area, accessible only by authorized personnel.

Randomization will be stratified by country and group: Group 1 (age 4 to less than 9 years); Groups 2 and 2a (age 1 to less than 4 years); Group 3 (age 6 months to less than 12 months); and Group 4 (age 6 weeks to less than 6 months). On Day 1, qualified subjects will be randomized using the IWRS to a formulation arm and number of doses depending on their age at the time of enrollment.

Randomization into groups and formulation arms will be restricted during various stages of the study as described previously in the protocol (section 6.1) based on DMC review of data from certain groups/arms prior to opening enrollment to other groups (see Section 11.1.1).

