### 13.1.3 Immunogenicity Analysis

The trial will evaluate the immunogenicity and safety of four formulations under different dosing regimens in 4 pediatric age ranges. Two cohorts of subjects will be enrolled into the trial. Cohort 1 will consist of 4 groups (4 to <9 years, 1 to <4 years [2 groups] and 6 months to <1 year), enrolled in age-step down fashion as described in Section 6.1. The youngest age group (Cohort 2, 6 weeks to <6 months) will be the last to complete enrollment. The factors under investigation, overall, and for each group include: formulation (4 formulation arms within each group); and number of doses (2 levels for each formulation within each group). For groups 1, 2, 2a, and 3 (in Cohort 1) the number of active doses will be 1 or 2 doses. For group 4 (Cohort 2), the number of active doses will be 2 or 3. Within each cohort, subjects are randomized to 1 of 8 trial arms (2 dose levels for 4 formulations), with group as a stratification factor.

Descriptive statistics for the primary, secondary and exploratory endpoints including estimates of seroresponse ( $\geq 4$ -fold rises), and 95% confidence intervals (CI) will be provided. Summaries will be provided by formulation arm (ie. combination of formulation arms and number of doses) and group (4 age ranges with Groups 2 and 2a in the same age range). Additional summaries will be provided at the cohort level, by pooling subjects across the relevant age groups in Cohort 1, as applicable.

Additional analyses will also be provided at the cohort level (pooling groups in Cohort 1). Statistical analyses of the primary endpoint will be performed for each cohort using the CMH method [36] stratified by group (in Cohort 1) to assess the effects of formulation/dose combination. Risk differences and corresponding 95% CIs will be provided for all pairwise comparisons of interest, without adjustments for multiplicity. The primary analyses will be based on the PPS.

Continuous secondary endpoints, such as GMT and GMFR, will be summarized descriptively by group for each of the 8 formulation/dose combinations.

Analysis of covariance (ANCOVA) will be conducted for selected continuous endpoints (such as GMT and GMFR), examining the effect of formulation/dose combination using the

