**Figure 4.a Schematic of Trial Design**

\* Recently manufactured clinical trial material lots

A total of 840 healthy subjects will be randomized to the following cohorts, with stratification by country and group:

- Cohort 1, N=480 (Group 1: aged 4 to less than 9 years; Group 2: aged 1 to less than 4 years; Group 2a: aged 1 to less than 4 years; Group 3: aged 6 months to less than 1 year [N=120 each]: subjects will be randomized with equal probabilities to 1 of the 8 unique combinations of formulation arms and dose groups (ie, 4 formulation arms and 1 or 2 doses). The additional 120 children, designated as Group 2a, are being included to evaluate the recently manufactured NoV bivalent VLP vaccine formulations prior to enrolling children in Groups 3 and 4. Each of the combinations will consist of approximately 15 subjects per group. Thus Cohort 1 consists of 480 subjects in Groups 1, 2, 2a, and 3 combined.
- Cohort 2 (Group 4: aged 6 weeks to less than 6 months): 360 subjects will be randomized to receive the recently manufactured NoV bivalent VLP vaccine with equal probabilities to 1 of the 8 unique combinations of formulation arms and dose groups (ie, 4 formulation arms and 2 or 3 doses). Each of the combinations will consist of approximately 45 subjects.
- This study plans to assess the immunogenicity and safety of the NoV bivalent VLP vaccine in children when given independently of the routine pediatric vaccines but, importantly, never to interfere with routine vaccine administration of children in each of the countries planned for evaluation. National pediatric vaccine regimens in children 6 weeks to 6 months of age vary by country (eg, routine pediatric vaccines may be given at 2, 3, and 4 months of age; 2, 4, and 6 months of age; or at 3, 5, and 12 months of age).

Subjects 6 months to less than 9 years of age (inclusive, Cohort 1) will receive either 1 or 2 doses by IM injection, at least 28 days apart (Days 1 and 29), in 4 groups comprising 3 age ranges (Group 1: aged 4 to less than 9 years; Group 2 and Group 2a: both groups aged 1 to less than 4 years; and Group 3: aged 6 months to less than 1 year). Infants 6 weeks to less than 6 months of age (Group 4/Cohort 2) will receive 2 or 3 doses by IM injection given approximately 56 days apart (Days 1, 56, and 112). Routine child and infant vaccinations will be given on schedule per the national guidelines approximately 28 days apart from the investigational vaccine in each age group.

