## **7.8 Immunogenicity Analysis**

### *General Methodology*

The primary population for immunogenicity analyses will be the PPS. Supportive immunogenicity analyses on primary and key secondary endpoints will also be performed using FAS.

Descriptive statistics for the primary, secondary, and exploratory endpoints will be computed for all available assays at all relevant time points and include the following:

- Titer values (eg, GMT, BT50, GMFR): geometric mean, GSD, 95% CIs, minimum, and maximum;
- Other continuous endpoints: mean, SD, median, minimum, and maximum;
- Categorical variable (eg, seroresponse rate): number and percentage of subjects, and 95% CIs in specified categories. The 95% CI of seroresponse rate will be calculated using exact (Clopper-Pearson) method.

Cohorts will be analyzed separately due to different number of doses (1 or 2 in Cohort 1; 2 or 3 in Cohort 2).

Analysis of covariance (ANCOVA) will be conducted for continuous outcome parameters (eg, GMT, GMFR), examining the effect of formulation/dose combination using log-transformed values of the endpoint as the dependent variable and the corresponding log-transformed baseline (pre-vaccination) value as a continuous covariate. The ANCOVA models will include group as a factor for analyses of Cohort 1 with a group by formulation/dose combination interaction term if

appropriate as follows. If the interaction term p-value is  $\leq 0.05$ , the term will remain in the model. If the p-value is  $>0.05$  it will be removed. For Cohort 1, the model will include estimates for treatment (formulation/dose combination) effect within each group, and at the cohort level across groups. A factor for country will be included in all models.

For binomial outcomes the Cochran-Mantel-Haenszel (CMH) method [2] for difference in proportions will be conducted, stratified by group (Cohort 1).

All pairwise comparisons (with the lower level as a reference group) will be presented, without adjustments for multiplicity.

Pre-specified comparisons of interest will be tested. The pre-specified comparisons of interest are the following:

- “A: 15/15, 1 Dose” vs. “A: 15/15, 2 Dose”
- “A: 15/15, 1 Dose” vs. “B: 15/50, 2 Dose”
- “B: 15/50, 1 Dose” vs. “C: 50/50, 1 Dose”
- “B: 15/50, 1 Dose” vs. “B: 15/50, 2 Dose”
- “C: 50/50, 1 Dose” vs. “B: 15/50, 2 Dose”
- “C: 50/50, 1 Dose” vs. “C: 50/50, 2 Dose”
- “C: 50/50, 1 Dose” vs. “D: 50/150, 2 Dose”
- “D: 50/150, 1 Dose” vs. “D: 50/150, 2 Dose”

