### 7.8.1 Primary Immunogenicity Endpoint(s)

The primary immunogenicity endpoint for this trial is seroresponse rate, defined as the percentage of subjects with a 4-fold rise or greater, in serum anti-NoV antibody titers for both GI.1 VLP and GII.4 VLP as measured by Pan-Ig ELISA at Day 57 (Cohort 1) and Day 140 (Cohort 2). The primary analyses will be based on the PPS data but will also be provided using the FAS.

The seroresponse rates and 95% CIs will be summarized (as described in the General Methodology of Section 7.9) for each of the 8 formulation/dose combinations (4 formulation arms; 1 and 2 [or 2 and 3] doses), by group. These summaries will also be provided at the cohort level (pooling subjects across groups in Cohort 1). The 95% CI of seroresponse rate will be

calculated using the exact (Clopper-Pearson) method. These summaries will be provided for the subjects in the PPS and FAS.

Statistical analyses of the primary endpoint will be performed at the cohort level using the CMH method stratified by group to assess the effect of formulation/dose schedule. Common risk differences and corresponding 95% CIs will be provided for all pairwise comparisons of interest, without adjustments for multiplicity. The 14 comparisons of interest (listed in the *General Methodology* of Section 7.8 above) will be tested.

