#### Secondary and Exploratory Continuous Immunogenicity Endpoints

The secondary and exploratory continuous immunogenicity endpoints are listed below:

- CCI
- 
- 
- 
- 
- 
- 
- 

GMT, BT50 and GMFR will be summarized descriptively, as described in the General Methodology of Section 7.9, for each of the 8 formulation/dose combinations (4 formulation arms; 1 and 2 [or 2 and 3] doses), by group, at each scheduled time point. These summaries will

also be provided at the cohort level, ie, by pooling subjects across the relevant groups. These summaries will be provided for the subjects in the PPS and FAS.

The GMT and BT50 will be calculated as the anti-logarithm of  $\sum(\log \text{transformed titer}/n)$ , ie, as the anti-logarithm transformation of the mean of the log-transformed titer, where n is the number of subjects with titer information. The GSD for GMT and BT50 will be calculated as the anti-logarithm transformation of the standard deviation of the log-transformed titer. The 95% CI will be calculated as the anti-logarithm transformation of the upper and lower limits for a two-sided CI for the mean of the log-transformed titers.

[figure not shown]
GMFR will be calculated as anti-logarithm of  $\sum (\log \text{transformed (post-vaccination titer/ pre-vaccination titer)}/n)$ . The GSD and 95% CIs for GMFR will be calculated similarly to those for GMT and BT50.

GMT, BT50 and GMFR will be analyzed with an ANCOVA model examining the effect of formulation/dose combination using the log-transformed value as the dependent variable and the corresponding log-transformed baseline value as a covariate. The ANCOVA models will include group as a factor for analyses of Cohort 1 with a group by formulation/dose combination interaction term included if appropriate, as follows. If the interaction term p-value is  $\leq 0.05$ , the term will remain in the model. If the p-value is  $>0.05$  it will be removed. For Cohort 1, the model will include estimates for treatment (formulation/dose combination) effect within each group, and at the cohort level across groups. A factor for country will be included. All the applicable pairwise comparisons will be provided with lower levels as the reference groups, with no adjustments for multiplicity. The 14 comparisons of interest listed in the *General Methodology* of Section 7.8 will be tested. The analyses will be based on the PPS.

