## **Section 7.8, Immunogenicity Analysis, General Methodology**

Prior Text:

Analysis of covariance (ANCOVA) will be conducted for continuous outcome *parameters*, examining the effect of formulation/dose combination using log-transformed values of the endpoint as the dependent variable and the corresponding log-transformed baseline (pre-vaccination) value as a continuous covariate. The ANCOVA models will *also* include *age* group as a factor for analyses of Cohort 1 with *an age group* by formulation/dose combination interaction *term as follows*. If the interaction term p-value is  $\leq 0.05$ , the term will remain in the

model. If the p-value is  $>0.05$  it will be removed. For Cohort 1, the model will include estimates for treatment (formulation/dose combination) effect within each age group, and at the cohort level across *age* groups. A factor for country will be included.

Amended Text:

Analysis of covariance (ANCOVA) will be conducted for continuous outcome parameters (eg, **GMT, GMFR**), examining the effect of formulation/dose combination using log-transformed values of the endpoint as the dependent variable and the corresponding log-transformed baseline (pre-vaccination) value as a continuous covariate. The ANCOVA models **will include group** as a factor for analyses of Cohort 1 **with a group** by formulation/dose combination interaction term if appropriate as follows. If the interaction term p-value is  $\leq 0.05$ , the term will remain in the model. If the p-value is  $>0.05$  it will be removed. For Cohort 1, the model will include estimates for treatment (formulation/dose combination) effect within each group, and at the cohort level **across groups**. A factor for country will be included **in all models**.

Reason for Change:

(1) clarify that country will be included as a factor in all models (2) change text to refer to group rather than age group, to clarify that group (4 groups [groups 2 and 2a with same age range]), not age range per se, is the factor of interest in the statistical model for Cohort 1 and (3) provide examples of continuous parameters

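### The primary seroresponse comparison leaves out country, a randomisation stratum. In Cohort 2 it is therefore unadjusted, with intervals wider than needed to the extent that seroresponse differs by country

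*SAP*

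**What the plan says.** **Randomisation.** Protocol 8.3: "Randomization will be stratified by country and group". SAP 4.4 agrees: "A total of 840 healthy subjects will be randomized to the following cohorts, with stratification by country and group".

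**Primary binary analysis.** SAP 7.8, General Methodology: "For binomial outcomes the Cochran-Mantel-Haenszel (CMH) method [2] for difference in proportions will be conducted, stratified by group (Cohort 1". SAP 7.8.1, on the primary endpoint: "Statistical analyses of the primary endpoint will be performed at the cohort level using the CMH method stratified by group". Protocol 13.1.3: "Statistical analyses of the primary endpoint will be performed for each cohort using the CMH method [36] stratified by group (in Cohort 1". For other dichotomous endpoints Protocol 13.1.3 names age as the stratifier. Country appears in none of these places.

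**Titre analysis.** The ANCOVA paragraph of SAP 7.8 closes with "A factor for country will be included in all models", and the ANCOVA paragraph of SAP 7.8.2 has "A factor for country will be included". Protocol 13.1.3 likewise puts a country factor in the ANCOVA.

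**Cohorts.** SAP 7.8 analyses the two cohorts separately because their dose numbers differ. Cohort 2 consists of Group 4 alone: 360 infants over eight arms, about 45 per arm (SAP 4.4). SAP 7.8.2 analyses seroresponse to both VLPs among the secondary and exploratory endpoints in the same way as the primary endpoint.

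**The concern.** A factor used to balance the randomisation would normally enter the main comparison as well. Here it enters the analysis of titres but not the analysis of seroresponse, which is derived from the same titres, and no reason is given. In Cohort 2 the only named stratifier has a single level, so a CMH risk difference reduces to the plain difference between two proportions.

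What is at stake is precision. Stratified randomisation keeps the arms balanced by country, so differences between countries contribute little to the real sampling error of the arm comparison. The unadjusted variance still counts them. If seroresponse varies by country, the reported intervals are wider than the data require. The primary objective is to select a formulation, and these are the intervals on the differences between formulations.

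A country effect is plausible but not shown. SAP 4.4 notes that routine infant vaccine schedules differ between countries, at the ages Cohort 2 enrols. That is a reason to allow for an effect, not evidence of one.

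**Working it through.** **1. Does the country sentence reach the CMH?** In SAP 7.8 the sentence on all models ends the ANCOVA paragraph. SAP 7.13 gives its purpose, "clarify that country will be included as a factor in all models", as a reason for changing that same paragraph. The CMH sentence follows on its own and names only group. SAP 7.8.1 and Protocol 13.1.3 repeat group alone. A programmer following 7.8.1 would leave country out.

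**2. The plan's own figures.** The plan gives no precision figure for the risk difference. Its only computed design figures are the adverse-event probabilities in Protocol Table 13-a. For a rate of 0.33% and N=480, 1 − (1 − 0.0033)^480 = 79.5%, as printed. They do not bear on this point.

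**3. Inputs.** From the documents: 45 per arm, equal allocation, 95% intervals, no multiplicity adjustment. Assumed, because the documents do not say: three countries of 15 per arm each, mean rate 50%, no arm difference.

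**4. Formula.** With country rates p_k and mean p̄:
- unadjusted half-width = 1.96 × √[2 p̄(1 − p̄)/45]
- country-stratified half-width = 1.96 × √[2 × mean{p_k(1 − p_k)}/45]

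Unadjusted: 1.96 × √(2 × 0.25/45) = 20.7 points. Extra children per arm = 45 × (0.25/mean{p_k(1 − p_k)} − 1).

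| Country rates (%) | mean p_k(1 − p_k) | Stratified half-width | SE ratio, unadjusted/stratified | Worth in extra children per arm |
|---|---|---|---|---|
| 50/50/50 | 0.2500 | 20.7 | 1.000 | 0 |
| 40/50/60 | 0.2433 | 20.4 | 1.014 | 1.2 |
| 30/50/70 | 0.2233 | 19.5 | 1.058 | 5.4 |
| 20/50/80 | 0.1900 | 18.0 | 1.147 | 14.2 |

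**5. Other assumptions.**
- Mean rate 70%, three equal countries: 18.9 unadjusted against 18.9 (70/70/70), 18.6 (60/70/80) or 17.7 (50/70/90).
- Two equal countries: 18.9 against 18.5 (60/80) or 17.0 (50/90).
- Uneven countries (25/12/8 or 30/10/5 per arm): the SE excess falls to 1.0–1.2% for 40/50/60 and 4.2–5.2% for 30/50/70.

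**6. Coverage by simulation (200,000 runs per scenario, 45 per arm, no arm difference).** The unadjusted Wald interval covers 95.2% (mean rate 50%) or 94.6% (mean rate 70%) with no country effect. It covers 94.9% at 60/70/80, 96.4% at 30/50/70 and 97.7% at 20/50/80. It is near nominal until the country spread is large.

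**7. Could per-protocol exclusions create bias?** Only if they differ by arm and country together. Take 40/50/60 with no true difference and exclusions of 20/10/0% in one arm and 0/10/20% in the other. The rates become (0.8×40 + 0.9×50 + 1.0×60)/2.7 = 50.74% and (1.0×40 + 0.9×50 + 0.8×60)/2.7 = 49.26%, a shift of 1.48 points. The same pattern gives 2.96 points at 30/50/70 and 4.44 at 20/50/80. Exclusions that depend on arm alone or on country alone give 0.

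**8. Cohort 1.** Country is omitted here too, though group is used. With about 15 per arm per group and three equal countries, each group-by-country stratum holds about 5 per arm. The simulated SE ratios (group only over group by country) are 1.000, 1.014, 1.060 and 1.151 for the four spreads.

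**The case against.** The strongest counter-case is that this is a conditional precision point in a descriptive trial. There is no power calculation or formal null hypothesis (SAP 6.0), no decision rule uses these intervals, and the per-arm rates with exact intervals are unaffected. Protocol and SAP agree with each other on group-only stratification. All of that stands. It limits the weight of the point but does not give a reason for leaving country out.

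The size is all assumption. That also stands: at 10 points either side the gain is about 0.3 point, and the larger figures need country rates as far apart as 20% and 80%.

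The SAP names no interval formula. It cites a methods paper on covariate-adjusted differences in proportions (SAP reference 2), whose content cannot be checked here. The widths above are therefore for standard intervals, not one the SAP specifies. The strata to be used are stated, however, and country is not among them.

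In Cohort 1 the objection is stronger. Strata of about 5 per arm, or fewer with more countries, are a sensible reason to limit CMH strata. SAP 7.12 also applies the final methods at the interim on Groups 1 and 2, so changing the main Cohort 1 method could break that consistency if the interim has been run. The documents do not show whether it has.

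Three stronger readings are tempting and not supported:
- A reader might infer that the Cohort 2 intervals are conservative as a matter of fact. They are so only if seroresponse differs by country, which no passage shows.
- A reader might infer bias. Randomisation protects the estimate, and the exclusion pattern in step 7 is not suggested anywhere. SAP 7.2 identifies major violations before unblinding, and SAP 7.8.1 repeats the primary analysis on the FAS.
- A reader might infer that Cohort 1 must be restratified in its main analysis. The sparse strata and the interim argue against that.

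**Conclusion.** The omission is clear from the text: country stratifies the randomisation and enters the ANCOVA, but not the primary seroresponse risk difference. In Cohort 2 that difference is therefore unadjusted. This does not bias it under randomisation, and its intervals are about nominal if country does not matter.

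If country does matter, they are wider than necessary by about 0.3, 1.2 or 2.7 points on a half-width of 20.7, for spreads of 10, 20 or 30 points either side of 50%. These figures rest on three equal countries and 45 per arm, and the number of countries and their rates are unknown. The change is worth making because it is cheap and uses a factor already in the design. Leaving it out would not invalidate the trial's conclusions.

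**What to change.** **Cohort 2.** In SAP 7.8 and 7.8.1, stratify the Mantel-Haenszel risk difference by country. Name an interval that holds in small strata, for example the stratified Miettinen-Nurminen score interval; it covered 95.0–95.4% in the Cohort 2 simulations, against 94.2–94.6% for the Sato variance. Apply the same method to the both-VLP seroresponse endpoints in SAP 7.8.2. The unadjusted difference can be kept alongside.

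**Cohort 1.** Keep the group-stratified CMH as the main analysis. Add a group-by-country version as a sensitivity analysis, with small countries pooled by a rule that uses enrolment counts only.

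**Wording.** State in SAP 7.8 whether the country sentence applies to the binomial analyses as well as the ANCOVA.

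**Cost.** A few SAP sentences and a little programming; no new data. If country is not prognostic, the variance loss is about 0.1–0.3% in Cohort 2. In the Cohort 1 sensitivity analysis it is 0.8–1.6%, or about 0.3% after pooling into two country strata.

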### 7.8.1 Primary Immunogenicity Endpoint(s)

The primary immunogenicity endpoint for this trial is seroresponse rate, defined as the percentage of subjects with a 4-fold rise or greater, in serum anti-NoV antibody titers for both GI.1 VLP and GII.4 VLP as measured by Pan-Ig ELISA at Day 57 (Cohort 1) and Day 140 (Cohort 2). The primary analyses will be based on the PPS data but will also be provided using the FAS.

The seroresponse rates and 95% CIs will be summarized (as described in the General Methodology of Section 7.9) for each of the 8 formulation/dose combinations (4 formulation arms; 1 and 2 [or 2 and 3] doses), by group. These summaries will also be provided at the cohort level (pooling subjects across groups in Cohort 1). The 95% CI of seroresponse rate will be

calculated using the exact (Clopper-Pearson) method. These summaries will be provided for the subjects in the PPS and FAS.

Statistical analyses of the primary endpoint will be performed at the cohort level using the CMH method stratified by group to assess the effect of formulation/dose schedule. Common risk differences and corresponding 95% CIs will be provided for all pairwise comparisons of interest, without adjustments for multiplicity. The 14 comparisons of interest (listed in the *General Methodology* of Section 7.8 above) will be tested.

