This trial NOR-202 in children aged 6 weeks to less than 9 years will evaluate the safety and immunogenicity of multiple formulations with different ratios of the antigenic VLP components of the bivalent vaccine. The formulations for NOR-202 are selected based on the initial and additional results obtained from the factorial design study NOR-107 in adults. Based on the additional NOR-107 results, the number of formulation arms is reduced from 8 in amendment N° 1.0 of the original protocol to 4 in this amended protocol.

The upper age cut-off for the NOR-202 trial was selected based on the assumption that the immune response in older children and adolescents aged 9 to <18 years is similar to the immune response observed in those aged 18 years and over. Therefore subjects aged 9 to ≥18 years, are not included in trial NOR-202.

The primary goals of this clinical trial are therefore to evaluate the immunogenicity and safety of 1 to 2 doses in children 6 months to less than 9 years of age and 2 to 3 doses in infants 6 weeks to less than 6 months of age with the IM NoV bivalent VLP vaccine using different dosages of the VLPs to obtain confirmation of dosage, and schedule in these age groups. In order to maintain the trial blind, a single injection of saline placebo will be administered as the final dose for the 1 dose group in Cohort 1 and for the 2 dose group in Cohort 2.

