Although the VLP manufacturer has changed, the vaccine dosages and regimens with the four vaccine formulations evaluated in Groups 1 and 2 will also be evaluated in children in Groups 2a, 3, and 4. However, only children in Groups 2a, 3, and 4, will receive the recently manufactured vaccine.

Enrollment in Group 2a will be initiated after all four vaccine formulations of the recently manufactured vaccine are released for clinical use.

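### In Cohort 1 the final between-arm analysis of the primary seroresponse endpoint is only a common risk difference over groups that span three age ranges and two VLP manufacturers

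*SAP*

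**What the plan says.** SAP 7.8.1 defines the between-arm analysis of the primary endpoint: "Statistical analyses of the primary endpoint will be performed at the cohort level using the CMH method stratified by group". The output is also set there: "Common risk differences and corresponding 95% CIs will be provided for all pairwise comparisons of interest, without adjustments for multiplicity". Protocol 13.1.3 describes the same analysis, for each cohort, with group as the stratification factor in Cohort 1. Below cohort level, 7.8.1 plans seroresponse rates with Clopper-Pearson intervals for the eight formulation/dose combinations in each group, but no differences between arms.

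Titres are treated differently. In SAP 7.8 (General Methodology) the Cohort 1 ANCOVA estimates the treatment "effect within each group, and at the cohort level across groups", and a group-by-arm interaction stays in the model if its p-value is 0.05 or less.

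The groups do not all receive vaccine from the same VLP source. Protocol 4.2 (rationale for Amendment 3) states that "only children in Groups 2a, 3, and 4, will receive the recently manufactured vaccine". Groups 1 and 2 had the original supply. Dosages and regimens are otherwise unchanged.

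The pooling set is described in two ways. SAP 4.4 and 7.1 describe Cohort 1 as four groups (1, 2, 2a, 3). A later paragraph of 7.1 says by-cohort summaries and analyses pool three age groups, given as groups 1 to 3.

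**The concern.** The primary objective is to select a formulation for further development in children. Protocol 4.2 describes the aim as "using different dosages of the VLPs to obtain confirmation of dosage, and schedule in these age groups". Vaccine for the later groups comes from the new manufacturer, and Group 2a was added to evaluate that vaccine.

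A single common risk difference over Groups 1, 2, 2a and 3 answers this directly only if the contrast between arms is about the same at each age and for both manufacturers. If it is not, the common value may describe no group. The plan allows for such variation in the secondary titre endpoints but not in the primary endpoint. At the final analysis, a reader judging formulations of the recently manufactured vaccine at 6 months to under 4 years would have no primary between-arm estimate with an interval for those children.

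**Working it through.** **Plan's own figure.** The documents give no precision or power figure for this contrast. The only sample-size table (Protocol 13.3, Table 13-a) concerns adverse events. It reproduces, for example 1 - (1 - 0.0033)^480 = 79.5%, but does not bear on this point.

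**Inputs from the documents.** Cohort 1 has 480 children in four groups of 120, randomised equally to eight combinations: 120/8 = 15 per arm in a group, 30 per arm in two groups, 60 per arm in four. Cohort 2 has 360/8 = 45 per arm. Response rates are not given, so those below are assumptions.

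**Weights.** The Mantel-Haenszel weight of a stratum is proportional to n1·n0/(n1 + n0). With 15 v 15 in each of four groups, every weight is 0.25, so the common risk difference is the plain average of the four group differences.

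**Precision.** 95% half-width = 1.96·√(2p(1 - p)/n), both arms at rate p, in percentage points:

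| Contrast | n per arm | p = 50% | p = 60% | p = 70% | p = 90% |
|---|---|---|---|---|---|
| Four groups pooled | 60 | 17.9 | 17.5 | 16.4 | 10.7 |
| One manufacturer (1+2 or 2a+3) | 30 | 25.3 | 24.8 | 23.2 | 15.2 |
| One Cohort 1 group | 15 | 35.8 | 35.1 | 32.8 | 21.5 |
| Cohort 2 (already planned) | 45 | 20.7 | 20.2 | 18.9 | 12.4 |

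**Example 1 (assumed rates).** Groups 1+2: 60% v 60%. Groups 2a+3: 50% v 80%.
- Groups 2a+3: SE = √((0.25 + 0.16)/30) = 0.117, so 30 points, 95% CI 7 to 53.
- Groups 1+2: difference 0, SE = √(0.48/30) = 0.126.
- Common: 0.5·0 + 0.5·30 = 15 points; SE = 0.5·√(0.117² + 0.126²) = 0.086, so 95% CI -2 to 32.

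**Example 2 (reference rate 50%).** +20 points in Groups 1+2 and -10 in Groups 2a+3 gives a common value of +5 (half-width 17.4). The value for Groups 2a+3 is -10 (half-width 25.0), so the signs differ.

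**Example 3 (reference rate 50%).** Differences of 0, +10, +10 and +40 in Groups 1, 2, 2a and 3 average to +15 (half-width 17.1), a value that no group has.

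**Would a homogeneity test reveal this?** In Example 1 the manufacturer contrast has z = 0.30/√(0.117² + 0.126²) = 1.74 (p = 0.08). At the 5% level the power is about 41% for a 1-df test by manufacturer and about 28% for a 3-df test across four groups.

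**If only groups 1 to 3 are pooled.** The estimate still mixes manufacturers, with two of its three strata on the original vaccine, and Group 2a has no part in any primary contrast.

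**The case against.** A reader might infer that the plan has no between-arm primary estimate for any age group or for the recently manufactured vaccine. The documents do not support that. Cohorts are analysed separately, and Cohort 2 is Group 4 alone: one age range, about 45 per arm, all on the recently manufactured vaccine. With one stratum its estimate is a plain risk difference. Group 4 does not replace the missing Cohort 1 contrasts, however. It is aged 6 weeks to under 6 months, receives 2 or 3 doses 56 days apart and is read at Day 140. Eight of the 14 listed pairs include a 1-dose arm, which Cohort 2 lacks.

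Nor did Groups 1 and 2 receive expired vaccine. Protocol 4.2 says they were dosed before expiry.

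Other objections carry weight:
- The by-group rates let a reader subtract one arm from another and see a reversal. They do not supply an interval for the difference.
- The Day 57 interim is split into Groups 1+2 and Groups 2a+3, with the final-analysis methods. SAP 7.12 allows it to be a subset of those analyses, so this output is not assured, and the final analysis has no such split.
- SAP 7.1 says that analyses are generally given by age group and by cohort. If that was meant to cover primary contrasts, 7.8.1 does not carry it through.
- The trial is descriptive, and no rule ties the choice of formulation to the common risk difference. The examples show what could be masked, not what will be.
- Stratified pooling is a standard choice for strata this small, and a homogeneity test has little power. Both points stand.

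**Conclusion.** The point holds for Cohort 1 at the final analysis. SAP 7.8.1 specifies only a common risk difference for the primary endpoint, over three age ranges and two manufacturers, with no difference by group or by manufacturer. It does not hold for Cohort 2.

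The size depends on how far the effects differ, which the documents cannot tell us. If they are alike across groups, nothing is lost and the pooled estimate is the most precise. If they differ as in the examples, the pooled value can halve the Groups 2a+3 effect or reverse its sign. These results assume equal arms of 15 per group, no exclusions from the per-protocol set, and the stated response rates. No power claim in the plan is affected, because none is made.

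**What to change.** In SAP 7.8.1, for the listed Cohort 1 pairs at the final analysis, add as descriptive output:
1. the stratified common risk difference with 95% CI by manufacturer (Groups 1+2; Groups 2a+3);
2. the risk difference with 95% CI within each group.

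State that, when formulations of the recently manufactured vaccine are judged, the Groups 2a+3 estimate is read together with Group 4. The by-manufacturer estimate still spans 6 months to under 4 years, so the within-group values belong beside it. A homogeneity test is optional; a non-significant result should not be taken as evidence of a common effect.

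Reconcile the three-group pooling sentence in SAP 7.1 with the four-group design, so that the place of Group 2a is explicit.

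The cost is SAP wording and extra table columns; no new data or subjects are needed. The drawback is the wide intervals in the table above, and more unadjusted comparisons to read with restraint.
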